We will always try to favor chemoembolization versus simple embolization. If the choice is simple embolization, it should be performed with particles of 500 microns maximum and until complete stagnation in the targeted arteries.

Desirable doses for chemoembolization injections

- **100 mg doxorubicin** (reconstituted in 5 mL or the smallest possible volume of fluid). Doxorubicin may be reconstituted in X-ray contrast medium to increase density and promote emulsion stability or 1500 mg of streptozotocin
- **10 ml of lipiodol ideally**
- **Spherical embolization particles: from 100 to 700 microns** depending on the operator's preference and should always be performed until complete stasis.

PREPARATION AND INJECTION TECHNIQUE

Chemoembolization

The use of loaded microspheres is not allowed chemoembolization must involve the use of an emulsion of doxorubicin or streptozotocin and Lipiodol

- Preparation of the emulsion with two 20CC uher lock syringes connected by a three-way valve. The mixing process should be initiated by pushing the doxorubicin or streptozotocin towards the Lipiodol (the aim is to promote a water-in-oil emulsion) and by making about 20 back and forth syringes. The mixture obtained must be injected before embolization under scopic control and with a flow rate avoiding arterial reflux.
- The use of a microcatheter is recommended in case of localized disease in order to obtain an ultra-selective positioning.
- It is imperative to try to perform the embolization in addition to the chemopiodol and therefore to stop the injection of the drug/Lipiodol emulsion before complete stagnation, or failing that to wait at least 10 minutes after injection of the chemopiodol to obtain a flow capable of allowing the embolization.
- Subsequent particle embolization should result in complete stasis in the targeted arteries at least to the second-order arteries in case of lobar involvement.

Embolization

The use of spherical embolization particles of 100 to 500 microns according to the

operators' choice. The injection is done in a slow way with spheres suspended in the saline/contracts mixture in order to avoid aggregation of particles responsible for proximal occlusions. Embolization is complete to the second and third order branches. Stasis should be observed for 10 minutes before deciding to terminate the procedure. There is no limitation in the volume of embolization that can be used.

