The description of clinical and medical variables will be done using percentages (95% confidence interval) and mean (standard deviation) and median (Min-Max) as well as the interquartile range (Q1-Q3).

Survivals and times will be estimated by the Kaplan Meier (KM) method. They will be described by medians and rates at different time points with their 95% confidence intervals. Median follow-up time will be calculated using the reverse Kaplan Meir method.

The results for the primary endpoint will also be described by a Water Fall plot representing for each patient the percentage change at 24 months in liver metastasis size since the measurement at inclusion according to the response according to the RECIST V1.1 criteria.

The time to onset of grade 3/4/5 toxicity will be estimated using the Kaplan Meier method.

Exploratory analyses

- research into factors predictive of progression-free survival and/or overall survival
- comparison of progression-free survival between embolization alone and chemoembolization

4. Independent committees

An independent committee will be formed and will include at least: two physicians (oncogastroenterologists), a statistician, a pharmacovigilance expert. The independent committee may meet at any time during the protocol when deemed necessary by the Sponsor.

XIII. JUSTIFICATION OF THE TEST

Neuroendocrine tumors (NETs) are a heterogeneous group of rare tumors. The prevalence of these tumors is estimated to be between 0.4 and 1 per 100,000 inhabitants per year. In the gastrointestinal tract, the most frequent locations are the appendix (19%), the small intestine (15%) and the rectum (11%). Neuroendocrine tumors of the small intestine mainly affect young adults between 30 and 35 years of age, while those of the colon tend to occur around 60 years of age [[1]].

Treatment of digestive endocrine tumors

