3.2.3 Exploratory analyses

An exploratory analysis is planned to:

- Search for factors predictive of progression-free survival and/or overall survival
- To compare liver progression-free survival between embolization alone and chemoembolization.

4 Study population

The study includes patients with well-differentiated metastatic NET of the gastrointestinal tract.

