5.7.2.2 Survival without liver progression

It is defined as the time from the date of inclusion to the date of first hepatic progression (based on centralized review or on the investigator's opinion in case of impossible review) or the date of death (regardless of cause). Living patients without hepatic progression will be censored at the point date or the date of last morphological evaluation.

Live patients for whom no morphological evaluation is available will be censored at inclusion date + 1 day.

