5.7.2 Exploratory analyses

- An analysis of the predictive factors for overall survival and progression-free survival will be performed;
- In an exploratory manner, the progression-free survival between embolization alone and chemoembolization will be compared (if the number of patients in each group is sufficient).

6 Study population for analysis

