7.6 Assessment of tolerance

7.6.1 Embolization or chemoembolization

Population ITT

Treatment by (chemo)embolization will be described by:

- The number of embolizations (1 vs 2) per patient and the total number of embolizations performed
- The number of chemoembolizations performed and the type: by doxorubicin or streptozotocin
- The number and percentage of patients who had (of the population of patients who had at least one embolization/chemoembolization):
 - 1 single embolization session
 - 1 single chemoembolization session
 - 2 embolization sessions
 - 2 sessions of chemoembolization
- Cross-tabulation of the number of embolizations or chemoembolizations planned in the PCR (at inclusion) and the number of embolizations or chemoembolizations actually performed.

Will also be described (percentage on the total number of embolisations and/or chemoembolisations performed):

- The territory of (chemo)embolisations
- The presence of a complication during the procedure (No vs. Yes), and if so:
 - presence of hepatic arterial occlusion by dissection or spasm (No vs. Yes)
 - presence of bleeding at the puncture site (No vs. Yes)
 - presence of another complication (No vs. Yes)
- The presence of a post-session complication (No vs. Yes), and if yes, a listing of these complications.

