7.7 Evaluations of exploratory analyses

- An analysis of predictive factors for overall survival and progression-free survival will be performed using univariate and multivariate Cox models. The predictive factors studied will be the parameters identified at inclusion:
 - Previous treatment (yes vs. no)
 - WHO (0 vs 1-2)
 - Age (< vs. \geq median)
 - Gender (Male vs Female)
 - Presence of carcinoid heart disease (yes vs. no)
 - Tumor grade (G1 vs G2)
 - Tumor site (appendix vs. jejunum/ileum vs. colon/rectum vs. other)
 - Bilateral liver metastases (yes vs. no)
 - Extrahepatic metastases (yes vs no)
 - BMI (< 25 vs \geq 25)
 - Chromogranin A ($>2N$ vs $<2N$ with N=200 ng/mL)
 - Decrease from Chromogranin A inclusion at M3 (2 thresholds will be tested: $>50\%$ vs $\leq50\%$ and $>30\%$ vs $\leq30\%$)
 - Decrease from baseline in urinary 5HIAA at M3 (2 thresholds will be tested: $>50\%$ vs $\leq50\%$ and $>30\%$ vs $\leq30\%$)
- As an exploratory measure, progression-free survival between embolization alone and chemoembolization will be compared by a logrank test (if the number of patients in each group is sufficient).

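### The exploratory embolisation versus chemoembolisation comparison is an unadjusted log-rank test between non-randomised groups, with conflicting endpoint wording and no rule for mixed-session patients

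*SAP*

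**What the plan says.** **Method.** SAP 7.7 says that "progression-free survival between embolization alone and chemoembolization will be compared by a logrank test". It labels this exploratory and makes it conditional on adequate numbers in each group, without giving a threshold. No covariates or strata are named. The Cox models in the same section list 13 candidate factors; technique is not one of them, and the models are not linked to this comparison.

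**Allocation.** SAP 5.3 states that nothing is randomised. Protocol VI.1 allows either technique and requires the modalities to be fixed before inclusion and written in the multidisciplinary meeting report. The same section adds: "We will always try to favor chemoembolization versus simple embolization".

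**Endpoint.** SAP 3.2.3 gives the aim as "To compare liver progression-free survival between embolization alone and chemoembolization". The second SAP section numbered 5.7.2 (Exploratory analyses) says "the progression-free survival between embolization alone and chemoembolization will be compared", and protocol XII.3 says "comparison of progression-free survival between embolization alone and chemoembolization"; neither mentions the liver. The SAP defines the two endpoints separately. For liver progression-free survival (5.7.2.2): "It is defined as the time from the date of inclusion to the date of first hepatic progression", or death. Progression-free survival (5.7.2.3) also counts extrahepatic progression.

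**Groups.** SAP 7.6.1 tabulates one embolisation, one chemoembolisation, two embolisations and "2 sessions of chemoembolization". It has no row for one of each.

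**The concern.** The groups form through planning decisions under a stated preference for one technique. If those decisions track prognosis, or differ between centres whose patients differ, an unadjusted test mixes that selection with any effect of technique. Baseline data that could reduce the problem are already collected: SAP 7.2.5 lists grade, bilateral liver metastases, percentage of liver invasion and extrahepatic metastases.

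The endpoint matters because both techniques act on the liver while patients may have extrahepatic disease, so the two endpoints could give different answers. With the endpoint and the grouping both open, the choice could be made after the data are seen.

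**Working it through.** **1. The plan's own figures.** None is given for this comparison. The primary design reproduces: 31 or more successes out of 68 gives a type I error of 0.046 at 35% and power of 0.802 at 50%; 68/0.95 = 71.6, hence 72. Only its 24-month rates are used below.

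**2. Events.**
- At 24 months with 50% event-free: 68 × 0.50 = 34, or 72 × 0.50 = 36.
- At 24 months with 35% event-free: 72 × 0.65 = 47.
- Follow-up continues to the SAP 5.6.1 point date (01/09/2017). Assume exponential times and uniform inclusion over the 34 months from November 2012, so follow-up runs from 24 to 58 months.
  - At 50%: λ = ln 2/24 = 0.0289; mean event-free share = (0.500 − 0.187)/(0.0289 × 34) = 0.318; 68 × 0.682 = 46 events.
  - At 35%: λ = 0.0437; share = (0.350 − 0.079)/(0.0437 × 34) = 0.182; 72 × 0.818 = 59 events.

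**3. Size of bias (prevalences and hazard ratio assumed).** For a factor with hazard ratio 2 and no technique effect, the approximate apparent hazard ratio is the ratio of mean hazards:
- 60% vs 30%: (0.6 × 2 + 0.4)/(0.3 × 2 + 0.7) = 1.6/1.3 = 1.23
- 60% vs 35%: 1.6/1.35 = 1.19

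**4. Effect on the test.** SE(log HR) ≈ 1/√(d·p(1−p)), with d events and share p in one group. The bias is ln 1.23 = 0.21.

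| Events | Split | SE | Bias/SE | Two-sided rejection at nominal 5% |
|---|---|---|---|---|
| 34 | 20/80 | 0.43 | 0.48 | about 8% |
| 47 | 50/50 | 0.29 | 0.71 | about 11% |

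More events would shrink the SE and raise these rates somewhat.

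**5. Simulation check.** 1,500 trials per setting, 72 patients, 36 months' follow-up, about 47 events, no technique effect, splits of 30/70 and 50/50:

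| Factor hazard ratio | Prevalence in the two groups | Rejection |
|---|---|---|
| 2 | 40% vs 40% | about 5% |
| 2 | 60% vs 35% | 9 to 10% |
| 2 | 70% vs 30% | 15% |
| 2.5 | 70% vs 30% | 22 to 23% |

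The last two rows show how the result moves with stronger imbalance. They are not estimates for this trial.

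**6. Precision.** Power ≈ Φ(√(d·p(1−p))·|ln HR| − 1.96). With 36 to 47 events and 10 to 50% treated by embolisation alone (assumed), power is 11 to 28% for a hazard ratio of 0.67 and 24 to 66% for 0.50. A non-significant p-value would say little; an interval would show how little.

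**7. Group definition.** SAP 7.7 names no population, so the ITT default of SAP 6.1.1 applies. Protocol VI.2 foresees embolisation being cancelled after inclusion, and protocol VII.1 bars a second session after certain toxicities. If groups were formed by sessions received, the cancelled patients would have no group and the grouping would use information from after inclusion, while time runs from inclusion. The modality planned before inclusion avoids both problems.

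**The case against.** The analysis is labelled exploratory, is gated on group size, and enters no decision: success depends on 31 of 68 patients. If chemoembolisation is favoured in practice, the test may never be run. All of this stands and limits the weight of the point.

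A reader might infer that embolisation alone is used when there is a clinical reason against chemoembolisation. The protocol states a preference but gives no reasons. Centre habit is equally compatible, and the protocol cites a 26-patient randomised trial that found no difference between the techniques. Confounding is therefore possible, not shown.

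A reader might also infer that the SAP groups by sessions received, or leaves mixed patients in neither group. No text says either. The SAP 7.6.1 list describes treatment delivery and does not define comparison groups. Embolisation alone can reasonably be read as no chemoembolisation at all, which puts mixed patients in the other group. What stands is that the assignment is not written down.

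The endpoint mismatch may be loose wording: SAP 7.4 and 7.5.2 also drop the liver qualifier where the liver endpoint is meant. That explains the conflict but does not settle which endpoint will be tested.

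**Conclusion.** The point holds as a minor one. An unadjusted log-rank between non-randomised groups could be biased, the endpoint is named in two ways, and mixed-session patients are not explicitly assigned. On the assumed inputs (prognostic hazard ratio 2, prevalence 60% against about 30 to 35%) the apparent hazard ratio is about 1.2 and the false-positive rate roughly 8 to 11% instead of 5%. The documents give no group split, no prevalence by technique and no prognostic hazard ratio, so these figures only illustrate scale.

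It would go too far to conclude that the p-value would simply reflect patient selection: under these inputs the bias is only 0.5 to 0.7 of a standard error. Nor does the point touch the primary endpoint or its decision rule.

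**What to change.** Amend the SAP before the database is frozen, as SAP 7.1.2 requires:

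- Reconcile SAP 3.2.3, the second 5.7.2 and 7.7 with protocol XII.3 on one prespecified endpoint. Liver progression-free survival would match SAP 3.2.3 and the primary endpoint; the choice is the sponsor's.
- Define the groups by the modality in the pre-inclusion multidisciplinary report, and state where a plan with both techniques goes. Check first that the planned type was captured: SAP 5.7.3 and 7.6.1 clearly tabulate only the planned number.
- Report a Cox hazard ratio with 95% CI, adjusted for a few prespecified baseline factors already collected, for example grade, liver involvement and extrahepatic metastases. Keep the log-rank as unadjusted description.
- Give a number for what counts as a sufficient group size.

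The cost is SAP wording, plus retrieval from the meeting reports if the planned type is not in the database. The sample size does not change. The downside is limited adjustment: at about ten events per parameter (an assumed convention), 34 to 47 events support three or four parameters including technique, slightly more with longer follow-up. Unmeasured reasons for choosing a technique remain, so the result stays exploratory.
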